## 1. Abbreviations

---

- (CCQ) – Clinical COPD Questionnaire
- (CDW) – VA Corporate Data Warehouse(ICD) - International Classification of Diseases
- (DC) - Discharge
- (EHR) – Electronic Health Record
- (GLMM) – Generalized Linear Mixed Model
- (IRB) – Institutional Review Board
- (MCS) – Mental Component Summary
- (PCP) – Primary Care Provider
- (PCS) – Physical Component Summary
- (SHEP) – Survey of Healthcare Experiences of Patients
- (VA) – Veterans Affairs
- (VISN) – Veterans Integrated Service Network
- (VR-12) – Veterans RAND 12 Item Health Survey

## 2. Funding/Regulatory

---

- Funding: Veterans Affairs (VA) Health Services Research and Development IIR 12-130-2
- IRB: VA Puget Sound Institutional Review Board (IRB) approved all study procedures.
- Trial registration: ClinicalTrials.gov as NCT02021955.

## **4. Background/Rationale**

---

Hospital admission and readmission have been an interest as an important driver of healthcare costs (AHRQ – [name]). In 2014, CMS implemented a COPD readmission penalty with assumptions that 30-day hospital readmissions were in part related to quality of care received while in hospital. Interest has focused on interventions to reduce COPD readmission with systematic reviews expressing doubt about the effectiveness of such interventions. From a patient perspective, exacerbations cause significant decrements in health-related quality-of-life. Across health systems, exacerbations drive health care expenditures with as many as half of patients requiring readmission within 6 months. The time after discharge (DC) for hospital can be viewed as a sensitive period where the likelihood of relapse peaks within 8 to 12 weeks after the incident exacerbation. How to deliver guideline recommended services in a timely fashion is a challenge across most health systems.

Within North America, the Department of Veterans Affairs provides care to Veterans at more than 1000 primary care settings and 150 medical centers. To meet the needs of Veterans across all instances of health care settings, VA needs to redesign care delivery systems regardless of locale. VA's current specialty care system reflects a fee-for-service model where specialists wait for patient referrals and do not assume responsibility for the health of a population of patients. This approach does not take advantage of the VA integrated health system increasing risk of care fragmentation. Specialists also are geographically concentrated at major medical centers that are culturally and physically separated from the patient's medical home. Determining how to deploy existing specialties using a primary care and patient centric approach represents an important opportunity to improve access, timeliness, and quality-of-care.

## **5. Rationale and objectives**

---

To be successful, health systems require a pragmatic health system-level solution. In this intervention, we propose to realign specialty care to collaborate with primary care teams and focus on patient needs and guideline concordance after discharge from hospital for COPD exacerbation. The intervention was designed to: 1) support primary care teams in the care of patients recently discharged for a COPD exacerbation, 2) utilize population health methods to identify patients at risk of readmission, 3) integrate proactive collaborative care

[figure not shown]
with specialty care and primary care teams 4) deliver care within the context of existing services and ongoing care, 5) leverage data systems and virtual care to facilitate improved delivery, and 6) respect the role of primary care while attempting to minimize their workload. Our goal is to improve 1) patient quality-of-life as measured by the Clinical COPD questionnaire and 2) reduce 180-day hospital readmission and mortality after hospital discharge.

## 6. Setting

We will conduct this trial at the VA Puget Sound Health Care System in Washington State, and the Boise VA Medical Center in Idaho. These are two academic medical facilities within VISN 20. We will include their accompanying 10 community-based outpatient clinics. These facilities cover a wide geographic range, including six that are designated as rural facilities.

## 7. Overall Design

Figure 2. Transition of primary care team clusters from control to intervention.

[figure not shown]
\*1-4 providers/team and 2-13 teams/cluster such that each cluster had comparable number of COPD patients

We will perform a modified stepped wedge clinical trial which is a variant of a clustered randomized cross-over design. Our focus will be to evaluate a multifaceted intervention designed to improve quality-of-life and decrease rate of hospital readmission and mortality among patients who were discharged from hospital with an exacerbation of COPD (Figure 2). We chose a modified stepped wedge design for several reasons: 1) resource constraints require a staggered roll out of the intervention; 2) timing is randomized, allowing all providers to eventually receive the intervention; 3) utilizes within and across provider comparisons maximizing efficiency and allowing the fewest number of providers to be enrolled because analyses utilize within provider and between provider comparisons increasing power.

In this stepped wedge design, clusters of teams transition from the control group to the intervention group over time. For this trial (Figure 2), we will assemble 30 clusters of primary care teams (see Section 8.4). Each primary care team consists of between 1-4 primary care clinicians. The number of primary care teams allocated to each cluster will be done to ensure a balanced number of patients with COPD in each cluster. All clusters of teams will start in the control group (first column of Figure 2). At the beginning of every 30-day period, a randomly selected cluster of primary care teams will transition to the intervention group such that all clusters will be in the intervention group in the 30th period (last column of Figure 2). The first control period (period 0) started on May 12, 2015.

We describe the trial flow in the following sections as illustrated in Figure 2.

Figure 2: Overall study flow

## 8. Provider Eligibility, Recruitment, and Consent

### 8.1. Eligibility:

We will obtain names and contact information for providers from the VA Corporate Data Warehouse (CDW). We will invite all PCPs (physicians, physician residents, physician's assistants, and nurse practitioners) from the VA Puget Sound and the Boise VA Medical Center to participate. The only exception will be PCPs who agreed to be co-investigators on this trial.

### 8.2. Recruitment:

We will approach providers using the following methods:

**Primary care team meetings:** We will introduce the study at primary care team meetings and grand rounds.

At the end of the presentation, we will ask providers to complete an enrollment sheet indicating their willingness, or not, to participate and a short demographic survey. Providers will either return the enrollment forms to trial staff after the meeting or mail it to us after the meeting. For providers who do not indicate their willingness, we will send an email inviting them to participate (see next section).

**Email:** We will invite providers via email if they do not return an enrollment sheet after a team meeting or if they are hired after the intervention launches. The email will contain an overview of the study, and a link to a detailed study description and the demographic survey, as well study contact information. The email will ask providers to review the material and reply if they wish to be excluded. The email explains that we will consider them enrolled in the study if they do not respond within one week (default opt-in), and that they could withdraw at any time.

### **8.3. Consent:**

We will consider a provider consented once they return the enrollment sheet, respond to the invitation email indicating that they want to participate, or we receive no response to the email within one week.

### **8.4. Provider clustering/randomization:**

We will group VA Primary care teams based on continuity and usual cross -coverage purposes. Primary care teams consist of 1-4 providers. We will group consented providers into 30 clusters. When assembling provider clusters, to the extent possible, we will group teams 1) that had shared staffing (e.g. nurses, medical support assistants), 2) are from the same site, and 3) when combined have relatively even distributions of empaneled clinic patients with a COPD diagnosis. By clustering this way, we minimize potential contamination of providers in the control arm by providers who had already crossed into the intervention.

The trial biostatistician will randomly assign each cluster to one of 30 30-day time periods. Each period the next cluster of PCP teams will transition from the control to the intervention period. When new providers join a primary care team, they assume their team's cluster and randomization time period. If providers change teams after randomization, they will retain their original cluster assignment. Any new teams created will be randomly assigned into one of the remaining intervention time periods such that they will have at least one time period in the control and intervention periods.

## **9. Index discharges**

---

An index discharge is the date of a hospital discharge involving care for COPD for a patient under the care of an enrolled provider starting May 12, 2015. We will interrogate the CDW daily to identify all eligible discharges as described below.

### **9.1. International Classification of Diseases (ICD) discharge diagnosis codes:**

We will define a COPD exacerbation as a primary ICD-9 primary discharge diagnosis of COPD (491%, 492%, 493.2%, or 496%), or a primary discharge diagnosis of respiratory failure (518.51, 518.53, 518.81, 518.83, 518.84) with any secondary diagnosis of COPD. In October 2015, VA will switch from the ICD-9 to the ICD-10 coding convention (J41.0, J41.1, J41.8, J42., J43.0, J43.1, J43.2, J43.8, J43.9, J44.0, J44.1, or J44.9 for COPD and J80., J96.00, J96.01, J96.02, J96.10, J96.11, J96.12, J96.20, J96.21, J96.22, J96.90, J96.91, J96.92 for respiratory failure).

We will exclude patients who were miscoded as having COPD discharge. Study coordinators will review the electronic health record (EHR) to confirm that the patient received care consistent with a COPD exacerbation. A single coordinator will review discharges where COPD is the primary discharge diagnosis. For cases of uncertainty, a second coordinator will review. If discordant, a study clinician will adjudicate and make the final decision.

Discharges for respiratory failure with a secondary COPD diagnosis are often more complicated. In this situation, two coordinators will independently review and adjudicate with a clinician when discordant.

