### **9.2. Discharges with missing ICD codes:**

For discharges with a missing ICD discharge code, we will employ a Natural Language Processing algorithm to identify potential index discharges. This algorithm identifies discharges with pre-defined keywords (%COPD%, %Bronchitis%, %Bronchiectasis%, %Bronchospasm%, %Emphysema%, %Acute% and %Bronc%, %SOB% and %Bronchitis%, %Chronic% and %Bronc%, %Chronic% and %Pulm%, %Chronic% and

%Obstruct%, Obstructive Pulmonary Disease, or Reactive Airway Disease) contained within the admission diagnosis or discharge summary text. Once identified, coordinators will review the EHR to confirm the hospitalization covered treatment for a COPD exacerbation.

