## 11. Blinding:

Because we will only review for recommendations patients whose PCP was in the intervention, it is not possible for anyone on the study team to be blinded for the intervention. Patient self-report outcomes collected over the telephone were collected by a coordinator blinded to the patient's intervention status.

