### 13.2. Sampling and non-response bias and missing data

We will perform an intention-to-treat analysis. The analysis will include all patients in the groups and time period which they were randomly assigned to begin receiving treatment, regardless of their adherence with the treatment and/or subsequent participation. An adjusted odds ratio will be estimated to compare control and intervention group odds of 180-day readmission or death, and adjustment mean differences will be estimated to compare control and intervention group means for CCQ Total Score and VR-12 PCS. In the event of missing outcome data, the primary analysis of the respective outcome will be based on outcome data imputed under a multiple imputation using chained equations procedure, with inference from 70 models of imputed data combined using Rubin's Rules. Sensitivity complete-case analyses will be performed for outcomes with missing values to assess whether direction of association or statistical significance is impacted by a change in missing data approach.

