## 6. DIFFERENTIAL DIAGNOSIS:

This hospitalization was due to COPD exacerbation:	Yes	Probably Yes	Probably No	No
				

If COPD Dx is questionable, list probable differential diagnosis:

\*\*\*\*\*

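### Chart review decides which discharges count after clusters are randomised, with no stated masking of phase and no planned check that exclusions are equal across phases

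*Combined protocol and SAP*

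**What the plan says.** Section 8.4 has the biostatistician randomise clusters to 30-day start periods. Under Section 9, discharges are identified afterwards by a daily query of the data warehouse.

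Section 9.1 fixes the diagnosis codes and then adds a judgement: "Study coordinators will review the electronic health record (EHR) to confirm that the patient received care consistent with a COPD exacerbation". Discharges that fail are removed: "We will exclude patients who were miscoded as having COPD discharge". The number of readers depends on the code:

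- Primary COPD code: "A single coordinator will review discharges where COPD is the primary discharge diagnosis". A second coordinator reads uncertain cases, and a study clinician settles disagreement.
- Respiratory failure with secondary COPD: "In this situation, two coordinators will independently review and adjudicate with a clinician when discordant".
- Missing code (Section 9.2): a keyword search finds candidates, then "coordinators will review the EHR to confirm the hospitalization covered treatment for a COPD exacerbation".

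Section 11 states that "it is not possible for anyone on the study team to be blinded for the intervention". The one masked task it names is telephone collection of patient-reported outcomes. Sections 9.1 and 9.2 say nothing about masking.

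Section 13.2 plans complete-case sensitivity analyses for missing outcomes. No section plans a count of chart-review exclusions by phase, or an analysis of discharges before that filter.

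**The concern.** When clusters are randomised first and patients are identified later, randomisation protects the comparison only if patients enter by the same rule in both phases. Here entry depends partly on a reading of the record by staff who may know the provider's phase.

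The decision also has different consequences by phase. Under Section 10.1, accepting an intervention-phase case starts abstraction, a team review, a note and order entry, and study coordinators do part of that work. Accepting a control-phase case starts none of it. The plan does not say that eligibility readers are separate from intervention staff.

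If borderline stays were accepted more readily in one phase, the two groups would differ in prognosis. The Section 13.1 model has a time spline, steroid days and prior outpatient exacerbations. Those terms cannot be relied on to remove a difference created by who was kept.

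**Working it through.** **The plan's own figure.** Inputs from Section 13.3: I = 30 clusters, N = 15 per cluster-period, risks 0.40 and 0.36, coefficient of variation 0.1, two-sided alpha 0.05. I take T = 31 (period 0 plus 30 steps) and the variance at the mean risk of 0.38.

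- σ² = 0.38 × 0.62 / 15 = 0.01571; τ² = (0.1 × 0.40)² = 0.0016.
- U = 1 + 2 + … + 30 = 465; W = V = 1² + … + 30² = 9455.
- Numerator: Iσ²(σ² + Tτ²) = 30 × 0.01571 × 0.06531 = 0.03077.
- Denominator: (IU − W)σ² + (U² + ITU − TW − IV)τ² = 4495 × 0.01571 + 71,920 × 0.0016 = 185.7.
- Variance = 0.0001657, so SE = 0.0129.
- Power = Φ(0.04/0.01287 − 1.96) = Φ(1.147) = 0.874, as stated.

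The power figure is not in dispute. It supplies the two yardsticks used below: a planned effect of 4 points and a planned SE of 1.29 points.

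**Effect of unequal exclusion.** The documents give no exclusion rate, no difference between phases and no event risk for excluded patients, so q and r below are assumptions. Suppose there is no true effect and the risk is 0.40 in both phases. If the intervention phase drops an extra share q whose event risk is r, the risk among those kept is (0.40 − q·r)/(1 − q).

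| q | r | Risk kept | Shift (points) |
|---|---|---|---|
| 0.05 | 0.25 | 0.408 | +0.8 |
| 0.05 | 0.50 | 0.395 | −0.5 |
| 0.05 | 0.60 | 0.389 | −1.1 |
| 0.05 | 0.70 | 0.384 | −1.6 |
| 0.10 | 0.25 | 0.417 | +1.7 |
| 0.10 | 0.50 | 0.389 | −1.1 |
| 0.10 | 0.60 | 0.378 | −2.2 |
| 0.10 | 0.70 | 0.367 | −3.3 |

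Example: (0.40 − 0.10 × 0.70)/0.90 = 0.33/0.90 = 0.367. If the extra exclusions fall in the control phase, the signs reverse.

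**What would imitate the whole planned effect.** Setting the risk kept to 0.36 gives q = 0.04/(r − 0.36): 28.6% at r = 0.50, 16.7% at r = 0.60 and 11.8% at r = 0.70.

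**Effect on the test.** With bias b, the two-sided error rate is Φ(−1.96 + b/SE) + Φ(−1.96 − b/SE).

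- At the planned SE of 0.0129, it is about 0.07 for b = 0.5 points and 0.41 for b = 2.2 points.
- Section 15 reports about 10 discharges per wedge. Reading a wedge as one 30-day period, that is roughly 300 over 30 periods. Assuming 150 per phase and ignoring clustering and time adjustment, SE = √(2 × 0.40 × 0.60/150) = 0.057. The error rates become about 0.05 and 0.07.

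So at the smaller size the false-positive rate barely moves, but the bias in the estimate is unchanged. An excess of 5-10% would then be only about 8 to 15 of 150 patients.

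**The case against.** The case for the plan has real content.

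- **Knowledge of phase is not established.** Sections 9.1 and 9.2 do not say what the reader sees. Section 11 explains the lack of blinding by the review for recommendations, which comes after eligibility. This stands: masking is unstated, but a reader should not infer that coordinators were shown to know phase, still less that they acted on it.
- **Discretion is limited.** Codes are fixed, the criterion concerns a hospital stay that precedes any recommendation, and harder cases get more readers and adjudication. This stands as mitigation. None of it masks phase, and a primary COPD code that raises no doubt in one reader gets no second reading.
- **Appendix 2, item 6.** The intervention team records its view on whether "This hospitalization was due to COPD exacerbation", and no equivalent is described for controls. A reader might infer a second, intervention-only route to exclusion. No text links the answer to removal, and the appendix's standard phrases for doubtful COPD suggest that such patients stayed in and received recommendations.
- **Intention to treat.** Section 13.2 says "The analysis will include all patients in the groups and time period which they were randomly assigned". A reader might see a contradiction with chart exclusions. There is none: removing ineligible records on pre-intervention information is compatible with intention to treat if done equally in both phases.
- **Timing.** Parts of the text are in the past tense, and Section 15 dates analysis decisions to December 2018, so masking may no longer be possible. Tabulation and reanalysis still would be.

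**Conclusion.** The point holds as a gap in safeguards, not as evidence of bias. Eligibility is judged after randomisation without stated masking of phase, and nothing planned would reveal unequal exclusion. Its size cannot be derived from the documents. The range of +1.7 to −3.3 points rests entirely on the assumed 5-10% excess in the intervention phase and the assumed risks of 0.25 to 0.70. The largest shift needs the extreme of both, and the direction is open. Within those assumptions no case reaches the full 4-point effect, but several reach a quarter or more of it. A cheap improvement is justified; a challenge to the trial's validity is not.

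**What to change.** 1. **Sections 9.1-9.2:** have coordinators record and lock the eligibility decision before cluster phase is joined to the case, where this is still possible. This is a query and workflow change for existing staff. Masking will be imperfect because the chart shows the primary care provider.
2. **Reporting:** tabulate chart-review exclusions by phase and reason. The cost is one table.
3. **Section 13.2:** add a sensitivity analysis of 180-day readmission or death in all algorithm-identified first discharges, meaning those found by ICD code plus the keyword-identified discharges of Section 9.2. Include them whether or not chart review confirmed them, and apply the Section 9.3 exclusions. Two details need stating:
   - How a patient is handled when an unconfirmed earlier stay changes the index discharge or its phase, since only the first discharge is analysed.
   - That the outcome comes from the data warehouse for everyone in this set. Section 13 names that source, while the record review and self-report also listed in Table 1 may not exist for unconfirmed patients.

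Miscoded patients will dilute any effect in the sensitivity set, so it serves as a check beside the primary analysis and does not replace it.

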### **9.2. Discharges with missing ICD codes:**

For discharges with a missing ICD discharge code, we will employ a Natural Language Processing algorithm to identify potential index discharges. This algorithm identifies discharges with pre-defined keywords (%COPD%, %Bronchitis%, %Bronchiectasis%, %Bronchospasm%, %Emphysema%, %Acute% and %Bronc%, %SOB% and %Bronchitis%, %Chronic% and %Bronc%, %Chronic% and %Pulm%, %Chronic% and

%Obstruct%, Obstructive Pulmonary Disease, or Reactive Airway Disease) contained within the admission diagnosis or discharge summary text. Once identified, coordinators will review the EHR to confirm the hospitalization covered treatment for a COPD exacerbation.

### **9.3. Additional eligibility criteria.**

- A patient may have more than one index discharge if the 180-day outcomes period for the prior index discharge is completed and was with a provider in the control group. Once a patient has a discharge with a provider in the intervention group, they cannot have additional index discharges. We will include each patient's first discharge only in primary analyses.
- We will exclude patients for whom we would not be able to provide recommendations including those discharged to a domiciliary unit, a nursing home, respite care, or to hospice.
- We considered patients discharged and readmitted within 12 hours to have a continuous hospital admission.

## **10. Intervention**

---

### **10.1. Recommendations for COPD guideline care:**

**Each week**, for patients with a new index discharge and under the care of a provider in the intervention group, we will perform the following:

**Chart abstraction:** A study coordinator will cut and paste pertinent sections of the EHR into an abstraction template ([Appendix 1](#)). These abstractions will include notations from emergency care, discharge summaries, primary care, pulmonary/sleep, social work, advanced directives, post-discharge telephone calls, and procedures and imaging studies.

**Clinical review:** The intervention team, consisting of pulmonary, primary care, and pharmacy providers, and study coordinators will convene to prepare recommendations for each patient with an abstraction as follows:

- Clinical lead:
  - A pulmonologist or PCP team member will be designated to lead the review each week
  - Reviews the abstractions, and/or EHR as needed, to draft a recommendations checklist ([Appendix 2](#)). The checklist will include:
    - Recommendations for diagnostic testing, medications, therapies/referrals, and/or follow-up, addressing any gaps in contemporary COPD guideline recommended care and related co-morbidities.
    - Draft of the recommendations note that will be placed into the EHR for the PCP's review.
- Review meeting:
  - Moderator: clinical lead.
  - Attendees: a clinical team consisting of at least one pulmonologist and one PCP, with input by the pharmacist as needed, and coordinators.
  - Review: the clinical team will discuss each patient's history, consulting the abstraction and EHR as needed, and identify any gaps in guideline COPD/comorbidity care.
- Recommendations:
  - Final recommendations: modify draft recommendations checklist as appropriate per team review
  - Language/content: ensure that notations will be acceptable to primary care providers. For example, smoking cessation counseling:

- Do not recommend if there have been notations reflecting previous discussions.
- Do offer recommendations such as addition of pharmacotherapy for smoking cessation if none has been previously offered.
- No recommendations: if a patient is receiving all guideline care, reinforce the excellent work.

**Entering recommendations and/or orders into EHR:** We will provide recommendations to the PCP timed to coincide with the patient's post-discharge clinic follow-up (usually within two weeks of discharge) as follows:

- EHR notation:
  - Enter note: a study coordinator will cut and paste the finalized recommendations note into the EHR as an E-Consult note for the lead clinician to sign.
  - Lead study clinician signs: once entered, the clinician will receive an EHR alert that they have a note ready for signature.
  - Additional signers: To ensure awareness, we will add the patient's PCP and pulmonologist, if any, as additional signers. If the PCP is a resident, we will add the attending physician as a signer.
  - Questions: The note will encourage the PCP to ask any questions about the recommendations, or any other elements of their OPD care, by responding with an addendum to the note, through encrypted email, or telephone.
- Enter unsigned orders:
  - A study coordinator will enter any recommended orders notated on the finalized recommendations checklist as an unsigned order on behalf of the PCP to sign.
  - For any questions that arise, the coordinator will seek guidance from the lead clinician.
- PCP reviews recommendations:
  - View alert: once entered, the PCP will receive an EHR alert that an order is awaiting signature.
  - Signs, modifies, or cancels orders: the PCP may choose to sign the order as is, modify the order, or decline the order as appropriate given their personal knowledge of the patient's clinical condition.
  - Autonomy: this process ensures the PCP maintains autonomous care of the patient.
- Recommendations requiring more clinical context:
  - We will elaborate on recommendations that require more clinical context in the E-consult note but will not enter any related orders on behalf of the PCP.

